10.0 LABELING, PACKAGING, STORAGE AND DISPOSITION OF CLINICAL SUPPLIES

10.1 Investigational Product

The investigator shall take responsibility for and shall take all steps to maintain appropriate records and ensure appropriate supply, storage, handling, distribution and usage of investigational product in accordance with the protocol and any applicable laws and regulations.

Clinical Supplies will be provided by Merck as summarized in Table 8.

Table 8 Product Description

Product Name & Potency	Dosage Form
pembrolizumab 100 mg/ 4mL	Solution for Injection

10.2 Packaging and Labeling Information

Clinical supplies will be affixed with a clinical label in accordance with regulatory requirements.

10.3 Clinical Supplies Disclosure

This trial is open-label; therefore, the subject, the trial site personnel, the Sponsor and/or designee are not blinded to treatment. Drug identity (name, strength) is included in the label text; random code/disclosure envelopes or lists are not provided.

10.4 Storage and Handling Requirements

Clinical supplies must be stored in a secure, limited-access location under the storage conditions specified on the label.

Receipt and dispensing of trial medication must be recorded by an authorized person at the trial site.

Clinical supplies may not be used for any purpose other than that stated in the protocol.

10.5 Returns and Reconciliation

The investigator is responsible for keeping accurate records of the clinical supplies received from Merck or designee, the amount dispensed to and returned by the subjects and the amount remaining at the conclusion of the trial.

Upon completion or termination of the study, all unused and/or partially used investigational product will be destroyed at the site per institutional policy. It is the Investigator's responsibility to arrange for disposal of all empty containers, provided that procedures for proper disposal have been established according to applicable federal, state, local and institutional guidelines and procedures, and provided that appropriate records of disposal are kept.

11.0 STUDY TERMINATION

Discontinuation of individual study participant treatment may occur for reasons including patient decision to withdraw from study, unacceptable toxicity, disease progression, or investigator or Principal Investigator determination that it is not in the patient's best interest to remain on trial.

The study may be terminated prior to completion of planned enrollment and achievement of objectives if there is evidence that the study regimen is not tolerable.

The IRB will be notified about the completion or early termination of the trial.

12.0 ADMINISTRATIVE AND REGULATORY DETAILS

12.1 Compliance with Trial Registration and Results Posting Requirements

Under the terms of the Food and Drug Administration Modernization Act (FDAMA) and the Food and Drug Administration Amendments Act (FDAAA), the Sponsor of the trial is solely responsible for determining whether the trial and its results are subject to the requirements for submission to the Clinical Trials Data Bank, <http://www.clinicaltrials.gov>. Information posted will allow subjects to identify potentially appropriate trials for their disease conditions and pursue participation by calling a central contact number for further information on appropriate trial locations and trial site contact information.

13.0 APPENDICES

13.1 ECOG Performance Status

Table 9 ECOG Performance Status

Grade	Description
0	Normal activity. Fully active, able to carry on all pre-disease performance without restriction.
1	Symptoms, but ambulatory. Restricted in physically strenuous activity, but ambulatory and able to carry out work of a light or sedentary nature (e.g., light housework, office work).
2	In bed <50% of the time. Ambulatory and capable of all self-care, but unable to carry out any work activities. Up and about more than 50% of waking hours.
3	In bed >50% of the time. Capable of only limited self-care, confined to bed or chair more than 50% of waking hours.
4	100% bedridden. Completely disabled. Cannot carry on any self-care. Totally confined to bed or chair.
5	Dead.

* As published in Am. J. Clin. Oncol.: *Oken, M.M., Creech, R.H., Tormey, D.C., Horton, J., Davis, T.E., McFadden, E.T., Carbone, P.P.: Toxicity And Response Criteria Of The Eastern Cooperative Oncology Group. Am J Clin Oncol 5:649-655, 1982.* The Eastern Cooperative Oncology Group, Robert Comis M.D., Group Chair.

13.2 Common Terminology Criteria for Adverse Events v5.0 (CTCAE)

The descriptions and grading scales found in the revised NCI Common Terminology Criteria for Adverse Events (CTCAE) version 5.0 will be utilized for adverse event reporting.
(https://ctep.cancer.gov/protocolDevelopment/electronic_applications/ctc.htm)

13.3 Response Evaluation Criteria in Solid Tumors (RECIST) 1.1 Criteria for Evaluating Response in Solid Tumors

RECIST version 1.1* will be used in this study for assessment of tumor response. While either CT or MRI may be utilized, as per RECIST 1.1, CT is the preferred imaging technique in this study.

* As published in the European Journal of Cancer:

E.A. Eisenhauer, P. Therasse, J. Bogaerts, L.H. Schwartz, D. Sargent, R. Ford, J. Dancey, S. Arbuck, S. Gwyther, M. Mooney, L. Rubinstein, L. Shankar, L. Dodd, R. Kaplan, D. Lacombe, J. Verweij. New response evaluation criteria in solid tumors: Revised RECIST guideline (version 1.1). Eur J Cancer. 2009 Jan;45(2):228-47.

13.4 High-Dose Interleukin-2 (HDIL-2) Administration and Toxicity Management Guidelines

13.4.1 Overview

The toxicities of HDIL-2 result from a capillary leak syndrome that results in initial vasodilation/decreased systemic vascular resistance followed by leakage of fluid and albumin into interstitial spaces. The initial manifestations are hypotension and tachycardia that may develop as early as 2 hours after the first dose, often after an initial rigor and fever. Later manifestations include generalized body edema, total body rash, diarrhea, nausea, mild confusion and potentially acute renal failure.

13.4.2 Specific Toxicities and Corrective Intervention

13.4.2.1 Hemodynamics

- Hypotension

- IV Fluids

Upon admission for HDIL-2 treatment, patients should be started on maintenance intravenous fluids in anticipation of ensuing capillary leak syndrome, vasodilation and decreased systemic vascular resistance. Colloid has no advantage over crystalloid, even when the albumin falls, and D5LR at 100cc/hr is recommended. Bolus IV fluids and increase in the continuous IV rate may be of value for initial management of hypotension to keep MAP > 60, attempting to limit the cumulative positive fluid balance by the end of 5 days to no more than 10% of the patient's dry weight by the end of each 5-day cycle of HDIL-2. This is accomplished by the judicious balance of fluids and vasopressor agents, depending on the patient's hemodynamic status, renal function, acid-base balance and pulmonary reserve.

- Vasopressor agents

If hypotension persists despite judicious fluid resuscitation, vasopressor support with an α -sympathomimetic agent (generally phenylephrine) is indicated. Titration of phenylephrine should be between 0.5 and 2mcg/kg/min to keep the systolic blood pressure over 80-90 mm Hg (MAP > 60). Since the BP nadir tends to occur 4-6 hours after each dose of HDIL-2, a "reserve" should be available in the vasopressor dose, so that additional doses of HDIL-2 should be given only if the phenylephrine dose can be weaned to below about 1 mcg/kg/minute before the next IL-2 dose.

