5.2.1.3 Definition of Dose-Limiting Toxicities

All toxicities will be graded using the National Cancer Institute (NCI) CTCAE v5.0 (Appendix 2; Section 13.2). Dose-limiting toxicity (DLT) assessment will be based on events occurring during the DLT assessment period, which is defined as course 1. Dose-limiting toxicities include all adverse experiences that are clearly not related to disease progression or intercurrent illness if judged by the investigator to be possibly, probably, or definitely related to study treatments that meet or exceed the following severity criteria:

- Toxicities associated with pembrolizumab representing autoimmune phenomenon have been extensively characterized, and may be exacerbated by combination treatment with IL-2. Treatment associated AE's that represent immune mediated pathology are codified in [Section 5.2.1.4](#), Table 4. For patients at Dose Level 1, all AE's resulting in Guideline recommendation for Treatment Discontinuation will also constitute a DLT.
- A delay in the scheduled administration of either component of therapy of > 21 days for pembrolizumab or SQ or IV bolus IL-2.
- Bolus IV dosing of IL-2 (Dose Level 2 and 3), especially at Dose Level 3, is known to be associated with acute severe toxicities. Doses are administered to patient tolerance according to established treatment guidelines (Appendix 4, Section 13.4). Toxicities associated with IL-2 administration will be initially managed according to the IL-2 Toxicity Management Guidelines (Appendix 4, Section 13.4). Toxicities that fail to stabilize within 48 hours of the last IL-2 dose or that fail to show improvement within 72 hours of the last IL-2 dose will convert to management according to [Section 5.2.1.4](#), Table 4 and resulting AE grade and Treatment Discontinuation assignment forming the basis for DLT determination.
- Grade 5 toxicity

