13.4.2.4 Cardiac

- Ischemia

Cardiac ischemia is also rare, but occasional focal myocarditis may occur, and arrhythmias or evidence of ischemia on EKG may mandate discontinuation of HDIL-2.

- Cardiac Arrhythmias

Atrial cardiac arrhythmias during HDIL-2 treatment are uncommon, but occasionally supraventricular tachycardia and atrial fibrillation may be seen. Careful assessment should be performed for supervening causes such as ischemia, myocarditis, pericardial effusion or pulmonary events. Treatment should include antiarrhythmic medications, and does not preclude continuation of HDIL-2. Serious ventricular arrhythmias are rare and warrant discontinuation of HDIL-2 and resumption only if a minor, reversible/treatable cause was found.

- Edema

Although patients often experience moderate amounts of peripheral edema at the end of each cycle, it is rare that they will experience severe symptoms from this extravascular fluid accumulation. Patients should be aggressively diuresed at the end of each cycle once they are hemodynamically stable.

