13.4.3 Dosing

HDIL-2 is administered as cycles of a maximum of 14 doses given at 8-hour intervals. Doses that are skipped for management of toxicities are not compensated by lengthening the cycle. As a general rule, if a patient has severe enough toxicity to withhold 2 or more consecutive doses, IL-2 will probably need to be discontinued for the rest of that 5-day cycle.

Organ-by-organ guidelines for IL-2 dosing must be individualized and considered in the context of the whole patient rather than in isolation. Each dose should be given or withheld after an assessment of the patient by the RN and house officer, with consultation from the principal investigator or the SCCA HDIL-2 team, if needed.

Table 10 Organ-by-Organ Toxicity Guidelines for Holding IL-2 Dosing

System	Generally Safe to Give HDIL-2 (one or more present)	Consider Holding HDIL-2 Dose (Especially if >1-2 criteria present)	Unsafe to Give HDIL-2 (any criterion present)
Cardiac	Sinus tach up to 130 bpm, occasional ventricular ectopy	Sustained sinus tach after correction of contributing factor such as fever, chills, hypotension or significant ectopy	Ischemic ECG changes, atrial fibrillation, SVT, ongoing VT, elevated CPK/troponin
Dermatologic	Rash	Urticaria	Moist desquamation, bullae
Gastrointestinal	Mild diarrhea controlled with antimotility agents, isolated bilirubin elevation	Severe nausea, emesis, marked elevation/rise of transaminases	Ileus/abdominal distension, severe pain, intractable emesis
Hemodynamic	Phenylephrine support up to 1mcg/kg/min	Phenylephrine support up to 1.5mcg/kg/min – must be stable or titrating down before next dose	Phenylephrine support >1.5mcg/kg/min and/or rising before next dose
Hemorrhagic/Thrombotic	Thrombocytopenia	Clinically significant bleeding requiring platelet transfusions	Life threatening bleeding or clot
Infection	UTI, viral URI or localized HSV	Bacterial infection contributing to hemodynamic compromise	Infection requiring surgical intervention, or unresponsive to antibiotics
Metabolic	Asymptomatic and correctable: hypokalemia, hypocalcemia, hyperglycemia, hypophosphatemia, hypomagnesemia,	Symptomatic electrolyte or metabolic disturbance	Arrhythmia or other life threatening consequence or metabolic disturbance

Neurologic	Mild somnolence, vivid dreams	Mild confusion, hallucinations, patient aware	Moderate – severe confusion, hallucinations, patient unaware or combative, seizures

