13.4.6 Monitoring

13.4.6.1 Monitoring guidelines: ICU routine

13.4.6.2 Labs:

- on admission (if not done on same day in clinic), CBC/plts/diff, PT/INR, chem. BMP/LFT/Mg/Phos,
- Daily CBC/plts/LFT/Mg/Phos
- Twice daily BMP
- At least every other day PT/INR

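### Appendix 4 sets two incompatible vasopressor conditions for giving the next IV IL-2 dose, and does not say whether an atrial arrhythmia must have resolved first

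*Combined protocol and SAP*

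**What the plan says.** Section 5.2.1.3 states that bolus IV IL-2 at Dose Levels 2 and 3 is given to tolerance under the guidelines of Appendix 4, section 13.4. Appendix 4 is therefore the operative dosing rule for those two levels.

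On vasopressor support, the narrative in section 13.4.2.1 says that additional doses "should be given only if the phenylephrine dose can be weaned to below about 1 mcg/kg/minute before the next IL-2 dose". Table 10 in section 13.4.3 grades the same situation in three columns. The generally safe column has "Phenylephrine support up to 1mcg/kg/min". The Consider Holding column has "Phenylephrine support up to 1.5mcg/kg/min", with the condition that it "must be stable or titrating down before next dose". The unsafe column starts above 1.5 mcg/kg/min, or when support is rising before the next dose.

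On cardiac rhythm, the unsafe column of Table 10, which applies if any one criterion is present, reads "Ischemic ECG changes, atrial fibrillation, SVT, ongoing VT, elevated CPK/troponin". Section 13.4.2.4, on supraventricular tachycardia and atrial fibrillation, says: "Treatment should include antiarrhythmic medications, and does not preclude continuation of HDIL-2". Table 13 in section 13.4.5 adds that, after correction of other factors and specific treatment, resuming IL-2 may be considered with or without antiarrhythmic drugs.

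Section 13.4.3 also says that skipped doses are not made up, that two or more consecutive withheld doses will probably end that cycle, and that the organ guidelines are to be individualized.

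**The concern.** Two passages of one appendix answer the same bedside question differently. The narrative sets a necessary condition, namely weaning to below about 1 mcg/kg/min. The table leaves dosing open up to 1.5 mcg/kg/min on a weaker condition, namely that support is not rising. Section 13.4.3 has each dose decided after assessment by the nurse and house officer, with the principal investigator or the institutional IL-2 team consulted if needed. Staff deciding every 8 hours should not have to choose between two rules.

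Patient safety comes first here, since these rules set how much IL-2 is given to a patient already on a pressor. The second stake is interpretive. Safety and tolerability are the primary objective, each dose level enrols 3 to 6 patients, and the number of IV doses tolerated is part of what a level's results describe. If that number depends partly on which passage was followed, it is harder to read.

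**Working it through.** The plan gives no figure to reproduce here, so the check is to set the passages side by side.

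**Vasopressor rule.** Inputs: the narrative condition in 13.4.2.1 and the three columns of the hemodynamic row in Table 10. The state is the phenylephrine rate when the next dose is due.

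| Phenylephrine, mcg/kg/min | 13.4.2.1 | Table 10 |
|---|---|---|
| Below about 1, not rising | Dose may be given | Generally safe |
| About 1 to 1.5, steady or falling | Dose not to be given | Consider holding; dosing left open |
| About 1 to 1.5, rising | Dose not to be given | Unsafe |
| Above 1.5 | Dose not to be given | Unsafe |

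The passages agree in three rows and conflict in the second. The disputed band is 1.5 − 1 = 0.5 mcg/kg/min wide. It lies inside the titration ranges that the appendix itself gives (0.5 to 2 in 13.4.2.1; 0.1 to 2 in Table 12), so patients on protocol support can be in it. The word about blurs the edge at 1, but it does not stretch to 1.5. Being steady and having been weaned below a level are also different tests: support held at 1.2 passes the table's condition and fails the narrative's.

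**Atrial arrhythmia rule.** Table 10 makes atrial fibrillation or SVT unsafe if present. Sections 13.4.2.4 and 13.4.5 allow IL-2 to continue or resume with treatment. The three passages can be read as one sequence: hold, treat, then consider resuming. No passage states that sequence, however, or says whether the rhythm must have resolved. Table 10 attaches the qualifier ongoing to ventricular tachycardia and not to atrial fibrillation or SVT, so its wording does not settle the matter. This is an ambiguity, weaker than the vasopressor conflict.

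**Possible effect on exposure.** Inputs: at most 14 doses per cycle at 8-hour intervals (13.4.3); 72,000 U/kg at Dose Level 2 and 600,000 U/kg at Dose Level 3 (Table 1).

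- Full cycle: 14 × 72,000 = 1,008,000 U/kg and 14 × 600,000 = 8,400,000 U/kg. Time from first to last dose: (14 − 1) × 8 = 104 hours.
- Smallest effect of a differing decision: one dose withheld and dosing then resumed. That is 1/14 = 7.1% of the cycle maximum, not made up later.
- Larger illustration, by assumption: the narrative reading leads to consecutive holds that end the cycle after dose k, while the table reading allows all 14. The share received is k/14: 29% for k = 4, 50% for k = 7, 71% for k = 10 and 86% for k = 12. At Dose Level 3 with k = 7, that is 7 × 600,000 = 4,200,000 against 8,400,000 U/kg.

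These shares show the largest divergence for each k and are not expected effects. Section 13.4.2.1 conditions the next dose on weaning; it does not itself end the cycle.

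**The case against.** The best defence is that Appendix 4 is guidance to be individualized. The narrative says should and about, and the table's middle column says only to consider holding. Withholding the dose between 1 and 1.5 mcg/kg/min therefore satisfies both passages. The protocol also names one site with an experienced IL-2 team, which limits divergent practice. All of this stands, and it is why the point concerns wording. It does not remove the contradiction: the table permits doses that the narrative's only-if condition excludes, and individual judgement needs one consistent rule to start from.

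On the arrhythmia passages, the defence is stronger. The word resuming in Table 13 presupposes a hold, and Table 10 speaks of a criterion being present. The hold, treat and resume reading is reasonable and may well be intended. What is missing is a phrase that says so.

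A reader might infer two stronger points that the documents do not support.

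- One is that the DLT assessment becomes ambiguous, because section 5.2.1.3 times it from the final dose: "Toxicities that fail to stabilize within 48 hours of the last IL-2 dose" convert to management under Table 4. The last dose is an observed event, whichever passage led to it, and its timing varies between patients by design because dosing is to tolerance. The conflict can change when the last dose falls, but no case has been shown in which the two readings give a different DLT result.
- The other is that the CPK and troponin criterion in Table 10 contradicts the inpatient laboratory list in 13.4.6.2 (for example "Daily CBC/plts/LFT/Mg/Phos"), which names neither test. A hold criterion does not imply a scheduled daily test. Section 13.4.6.1 sets ICU-routine monitoring, section 7.2 allows unscheduled procedures, and the flow chart places troponin in weeks 1 and 4, the weeks in which IV IL-2 is given.

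**Conclusion.** The vasopressor contradiction is real and lies in current, operative text. For a patient whose phenylephrine support is steady or falling between about 1 and 1.5 mcg/kg/min when the next dose is due, section 13.4.2.1 bars the dose and Table 10 leaves it open. The atrial fibrillation and SVT wording is a secondary ambiguity that a short clarification would resolve.

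The conflict can change how many IV doses a patient receives, by at least one of 14 per cycle wherever the two readings lead to different decisions. The overall size cannot be computed, because the documents do not say how often patients are in the disputed band or which passage staff would follow. The larger exposure shares above rest on the stated assumption that one reading ends the cycle early. No effect on DLT classification or on the escalation decision is shown. The point should be corrected because it is a patient-safety inconsistency in the rules that govern Dose Levels 2 and 3.

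**What to change.** The clinical team should reconcile section 13.4.2.1 with the hemodynamic row of Table 10, so that one instruction applies to a patient between about 1 and 1.5 mcg/kg/min. It should likewise reconcile section 13.4.2.4 and Table 13 with the cardiac row of Table 10, and say whether atrial fibrillation or SVT must have resolved before IL-2 continues. Appendix 4 should also state which governs, narrative or table, if they differ. Which threshold or rhythm rule is right is a clinical decision, and none is proposed here.

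The cost is a wording amendment to Appendix 4. Sample size, escalation rules, data collection and analysis do not change.

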13.4.2.2 Renal

- Oliguria

Oliguria is universal and is due to the combination of hypotension/hypoperfusion and decreased intravascular volume. It may be amplified in uninephric patients and patients on vasopressors. Oliguria per se is not an indication for fluids or diuresis; a bladder scan or urinary catheter may be useful to better assess the renal status if the patient is anuric, acidotic or has other reasons for urinary retention.

13.4.2.3 Pulmonary

- Hypoxia

The need for supplemental oxygen will vary among patients depending on their underlying lung function and disease. Supplemental oxygen should be used to keep the patient's oxygen saturation > 90-92%, and intravenous volume should be limited in patients whose oxygenation is difficult to maintain and in those with significant crackles and/or chest radiographic findings of pulmonary edema or significant pleural effusion.

- Cardiogenic Pulmonary Edema

Cardiogenic pulmonary edema is extremely rare in patients receiving HDIL-2 since patients are well-screened and HDIL-2 rarely causes global cardiomyopathy. Any patient with sudden pulmonary decompensation should be evaluated for causes of cardiac origin.

13.4.2.4 Cardiac

- Ischemia

Cardiac ischemia is also rare, but occasional focal myocarditis may occur, and arrhythmias or evidence of ischemia on EKG may mandate discontinuation of HDIL-2.

- Cardiac Arrhythmias

Atrial cardiac arrhythmias during HDIL-2 treatment are uncommon, but occasionally supraventricular tachycardia and atrial fibrillation may be seen. Careful assessment should be performed for supervening causes such as ischemia, myocarditis, pericardial effusion or pulmonary events. Treatment should include antiarrhythmic medications, and does not preclude continuation of HDIL-2. Serious ventricular arrhythmias are rare and warrant discontinuation of HDIL-2 and resumption only if a minor, reversible/treatable cause was found.

- Edema

Although patients often experience moderate amounts of peripheral edema at the end of each cycle, it is rare that they will experience severe symptoms from this extravascular fluid accumulation. Patients should be aggressively diuresed at the end of each cycle once they are hemodynamically stable.

